2.3 Potential Risks and Benefits

2.3.1 Potential Risks

This protocol will immunize children and adult participants with either IIV4 (IM) or LAIV4 (intranasal) vaccines that are licensed for use in the age groups studied. The discomforts of this study are those of receiving IM injection or intranasal application of

the vaccine, and blood drawn from an arm vein, and possible reactions to the vaccine and collection of the mucosal tissue using a nasopharyngeal swab. Drawing blood causes transient discomfort and may cause fainting. Infection at the site where blood will be drawn or where the vaccination is given is extremely unlikely, but is a potential risk. Bruising at the site of blood drawing may occur, but can be prevented or lessened by applying pressure for several minutes immediately after the blood draw. Immediate allergic reactions to vaccine, including anaphylaxis, are in general extremely rare (approximately 1 person in 4,000,000), and might occur as a skin rash such as hives, difficulty breathing, fainting, drop in the blood pressure and death. Such reactions can usually be stopped by emergency medications administered by study personnel. Vaccine recipients may develop systemic reactions such as fever, headaches, body aches, and fatigue. These reactions are usually greatest within the first 24 to 72 hours after vaccination and last 1 to 2 days. Analgesics (*e.g.*, aspirin or Tylenol®) and rest will generally relieve or moderate these symptoms. Other hypersensitivity reactions, including Arthus reactions resulting in large local swelling reactions, are also possible. Although Guillain-Barré syndrome may have been associated with the 1976-77 inactivated swine influenza vaccine and TIV vaccines used in early 1990's, subsequent inactivated vaccines have not been associated with an increased risk of this condition. Persons who care for severely immunosuppressed persons who require a protective environment should not receive LAIV, or should avoid contact with such persons for 7 days after receipt, given the theoretical risk for transmission of the live attenuated vaccine virus to close contacts. It is not known whether LAIV4 (FluMist Quadrivalent) is excreted in human milk. Because some viruses are excreted in human milk, a lactating woman is not eligible to be enrolled in Group F.

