5.2 Subject Exclusion Criteria for Enrollment and Subsequent Annual Vaccinations

1. Prior off-study vaccination with the current year's seasonal influenza vaccine
2. Receipt of LAIV in the prior season (does not apply to Groups F and G)
3. Received flu immunizations in 2 or more prior flu seasons (does not apply to Groups F and G)
4. Allergy to egg or egg products, or to vaccine components, including gentamicin, gelatin, arginine or MSG (if will be given LAIV4)
5. Life-threatening reactions to previous influenza vaccinations
6. Asthma in adults. Children aged 2 through 4 years who have asthma or who have had a wheezing episode noted in the medical record within the past 12 months, or for whom parents report that a health care provider stated that they had wheezing or asthma within the last 12 months [If yes, not eligible for LAIV Groups A, B, C, & F].
7. Active systemic or serious concurrent illness, including febrile illness on the day of vaccination
8. History of immunodeficiency (including HIV infection)
9. For children or adolescents through 17 years of age: receiving aspirin therapy or aspirin-containing products [If yes, not eligible for LAIV Groups A, B, C, and F].
10. Known or suspected impairment of immunologic function, including, but not limited to, clinically significant liver disease, diabetes mellitus treated with insulin, moderate to severe renal disease, or any other chronic disorder which, in the opinion of the investigator, might jeopardize volunteer safety or compliance with the protocol.
11. Blood pressure >150 systolic or >95 diastolic at first study visit and the day of vaccination (for children 12 yrs and older, and adults).
12. Hospitalization in the past year for congestive heart failure or emphysema.
13. Chronic Hepatitis B or C
14. Recent or current use of immunosuppressive medication, including systemic glucocorticoids (corticosteroid nasal sprays and topical steroids are permissible in all groups; inhaled steroid use is not permissible)
15. Persons who care for severely immunosuppressed persons who require a protective environment should not receive LAIV, or should avoid contact with such persons for

- 7 days after receipt, given the theoretical risk for transmission of the live attenuated vaccine virus to close contacts. [If yes, may be ineligible for Groups A,B, C and F].

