16. Malignancy, other than squamous cell or basal cell skin cancer (includes solid tumors such as breast cancer or prostate cancer with recurrence in the past year, and any hematologic cancer such as leukemia).
 17. Autoimmune disease (including rheumatoid arthritis treated with immunosuppressive medication such as Plaquenil, methotrexate, prednisone, Enbrel) which, in the opinion of the investigator, might jeopardize volunteer safety or compliance with the protocol
 18. History of blood dyscrasias, renal disease, or hemoglobinopathies requiring regular medical follow up or hospitalization during the preceding year
 19. Use of any anti-coagulation medication such as Coumadin or Lovenox, or anti-platelet agents such as aspirin (except up to 325 mg. per day), Plavix, or Aggrenox must be reviewed by investigator to determine if this would affect the volunteer's safety.
 20. Has taken an influenza antiviral medication within 48 hours prior to study vaccination [If yes, may not eligible for LAIV Groups A, B, C and F if unable to reschedule study vaccination].
 21. Receipt of blood or blood products within the past 6 months or planned used during the study
 22. Medical or psychiatric condition or occupational responsibilities that preclude participant compliance with the protocol
 23. Receipt of inactivated vaccine 14 days prior to study enrollment, or planned vaccinations prior to completion of last study visit
 24. Receipt of live, attenuated vaccine within 60 days prior to enrollment of planned vaccination prior to completion of last study visit
 25. Need for allergy immunization (that cannot be postponed) during the study period
 26. History of Guillain–Barré syndrome
 27. Pregnant woman
 28. Breastfeeding [If yes, not eligible for LAIV Group F]
 29. Use of investigational agents within 30 days prior to enrollment or planned use during the study
 30. Donation of the equivalent of a unit of blood within 6 weeks prior to enrollment or planned donation prior to completion of the last visit
 31. Any condition which, in the opinion of the investigator, might interfere with volunteer safety, study objectives or the ability of the participant to understand or comply with the study protocol.

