6.4 Concomitant Medications

At each study visit, the participant will be questioned about any vaccinations they have received or concomitant medication use, and the information will be recorded. Medication history will include medications taken within 28 days prior to enrollment and currently taken prescription and over-the-counter medications used throughout the study period. The investigator should be consulted regarding eligibility if the participant is taking oral steroid medications or medications for treatment of autoimmune disease (such as Plaquenil, methotrexate, prednisone, Enbrel), anti-coagulation/anti-platelet medications such as Coumadin, Lovenox, aspirin (except aspirin up to 325 mg. per day), Plavix, Aggrenox, or any other medications which might indicate a condition that precludes participant compliance with the protocol.

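### Aspirin wording is not reconciled: section 2.3.1 names it for post-vaccination symptoms with no age or vaccine limit, while exclusion item 9 bars users through age 17 from the LAIV groups, and its reach beyond Day 0 is unclear

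*Combined protocol and SAP*

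**What the plan says.** Four places in the combined protocol and SAP mention aspirin.

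- **Section 2.3.1 (Potential Risks)** opens with "This protocol will immunize children and adult participants with either IIV4 (IM) or LAIV4 (intranasal) vaccines". After describing systemic reactions, it adds: "Analgesics (*e.g.*, aspirin or Tylenol®) and rest will generally relieve or moderate these symptoms". Neither age nor vaccine limits that sentence.
- **Section 5.2, item 9** concerns people through 17 years: "receiving aspirin therapy or aspirin-containing products [If yes, not eligible for LAIV Groups A, B, C, and F". It has no dose threshold. The IIV4 groups (D, E and G) are not named.
- **Section 5.2, item 19** calls for investigator review of anti-coagulants and "anti-platelet agents such as aspirin (except up to 325 mg. per day"). It has no age limit.
- **Section 6.4 (Concomitant Medications)** has the investigator consulted on eligibility for a list of drugs that includes "Coumadin, Lovenox, aspirin (except aspirin up to 325 mg. per day), Plavix, Aggrenox". It also has no age limit.

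On timing, the governing heading is "5.2 Subject Exclusion Criteria for Enrollment and Subsequent Annual Vaccinations". Appendix B marks eligibility at Day 0 only. Section 7.6.1, the Dose 2 visit, lists a review of medications and the memory aid, a temperature, and vaccination with the same vaccine type as Dose 1. The footnote to Appendix A moves Group D children to LAIV4 when they turn 2, unless a contraindication has developed.

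**The concern.** The plan treats aspirin use by a minor as a reason not to give the live vaccine. It then names aspirin, with no age qualifier, as relief for symptoms that it says are greatest in the first 24 to 72 hours after vaccination. A reader of section 2.3.1 alone would not learn that aspirin matters for a child in an LAIV group. A reader of section 6.4 alone would not learn that item 9 has no dose threshold for minors.

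Two decisions are at stake. One is what families and staff understand about aspirin around a live-vaccine dose. The other is whether different staff would reach the same eligibility decision for a child taking low-dose aspirin at Dose 2, or for a Group D child at the switch to LAIV4. This is a matter of participant safety and consistent conduct, with no bearing on endpoints.

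**Working it through.** The plan gives no figure to reproduce. The check compares the passages and then counts places.

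**1. Scope of each aspirin statement**

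| Place | Who | Vaccine | Dose limit | Subject |
|---|---|---|---|---|
| 2.3.1 | children and adults | either | none | symptoms after vaccination |
| 5.2 item 9 | through 17 years | LAIV Groups A, B, C, F | none | eligibility |
| 5.2 item 19 | no age limit | not limited | up to 325 mg/day excepted | investigator review of anti-coagulant and anti-platelet drugs |
| 6.4 | no age limit | not limited | up to 325 mg/day excepted | investigator consultation on eligibility |

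A child in an LAIV group falls within all four rows. Items 9 and 19 stand in the same list, and section 6.4 also concerns eligibility, yet neither exception refers to item 9. Section 2.3.1 does carry other LAIV restrictions forward in the same paragraph (carers of severely immunosuppressed persons, and lactating women in Group F), but not item 9.

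**2. When item 9 applies**

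- Enrollment (Day 0): yes, by the section 5.2 heading and Appendix B.
- Annual return: yes, by the section 5.2 heading.
- Dose 2 at Day 28-32 (vaccine-naïve children in Groups A, B and C): not stated. Dose 2 is neither enrollment nor an annual vaccination, Appendix B shows no eligibility check there, and section 7.6.1 lists none. Section 5.3.2 speaks of withholding product under the exclusion criteria at the first visit.
- Group D after the switch to LAIV4: the section 5.2 criteria are applied at each annual return, but the consequence in item 9 names only Groups A, B, C and F. The Appendix A footnote relies on a contraindication and does not say whether item 9 counts as one.
- Use after vaccination: no passage in the available text says whether item 9 has any bearing.

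**3. Number of places concerned** (maximum group sizes, section 4)

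- LAIV4 places: A 6 + B 20 + C 20 + F 40 = 86.
- For children aged 13 or under: A 6 + B 20 + C 20 + F 20 = 66; 66/86 = 77%.
- Group D children who may switch to LAIV4: up to 6 more.
- Possible LAIV4 Dose 2 in the first season: A 6 + B 20 + C 20 = 46 at most. Only vaccine-naïve children need it. Inclusion item 6 also admits children with one prior season of IIV, and the documents do not say how many of each are expected.

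**The case against.** The strongest reply is that this is a loose example in background text. Section 2.3.1 describes what generally helps and directs nobody to give aspirin. Item 9 governs eligibility before vaccination, so the two passages address different moments. Section 6.4 requires medication use, including over-the-counter products, to be asked about and recorded at each visit, so aspirin use would be captured. The consent pages and the season-specific FluMist inserts (Appendix C) are not in the available text and may deal with the point. All of this stands, and it limits the weight of the concern.

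Four stronger readings are tempting, and the documents do not support them.

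- **That the protocol waives aspirin up to 325 mg per day in children.** In both item 19 and section 6.4, the exception spares the drug from investigator review or consultation as one of the anti-coagulant or anti-platelet drugs. Item 9 is a separate criterion and still applies.
- **That aspirin taken for early symptoms leads to Dose 2 in a child whom item 9 would have excluded.** Item 9 is in the present tense ("For children or adolescents through 17 years of age: receiving aspirin therapy or aspirin-containing products"). Section 2.3.1 says reactions last 1 to 2 days. A child given aspirin then is not, on that fact alone, receiving it at Day 28-32. The 28-day look-back in section 6.4 is for recording medication history and is not an exclusion window.
- **That parents are told to use aspirin.** Section 7.2 describes the Memory Aid as a diary with instructions about serious adverse events. What families are told about analgesics cannot be seen.
- **That annual returns are unprotected.** The section 5.2 heading covers them.

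What the reply does not remove is the unqualified example in a section covering children, the missing cross-references, and the silence on Dose 2 and on switched Group D children. General investigator discretion (item 31, section 5.3.2) does not tell staff how to treat low-dose aspirin in a child at those points.

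**Conclusion.** The concern holds as an unreconciled inconsistency on a participant-safety matter. It is not a rule that admits children on aspirin to live vaccination. The wording concerns up to 66 of 86 LAIV4 places (77%), plus up to 6 switched Group D children. The Dose 2 gap concerns at most 46. These are ceilings built on maximum group sizes. They do not estimate how many children would take aspirin, and they say nothing about harm. There is no effect on sample size, endpoints or analysis. The conclusion assumes that the consent form, Memory Aid and package inserts, which were not available, do not already settle the matter. Even if they do, the protocol's own passages still need to agree. The change is worth making because it is specific, concerns children given a live vaccine, and costs almost nothing.

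**What to change.** Reconcile section 2.3.1, items 9 and 19 of section 5.2, and section 6.4 so that the aspirin wording is consistent by age and vaccine, with cross-references to item 9 where the 325 mg per day exception appears. Carry the same wording into the consent form and Memory Aid instructions. State explicitly whether item 9 applies (a) to use after vaccination, (b) at LAIV4 Dose 2 in Groups A, B and C, and (c) to Group D children switched to LAIV4, and make section 7.6.1 and Appendices A and B agree with the answer. Which rule is correct is for the investigators; this point asks only that the passages agree and their reach be stated.

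The cost is a wording amendment to the protocol and participant materials, with IRB submission. Reconciling the text needs no new visit, sample or procedure.

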2.3.2 Known Potential Benefits

Participants given the seasonal influenza vaccine are likely to experience decreased frequency and severity of subsequent influenza infection. The beneficial role of influenza vaccination has been recognized increasingly over the past several years as more information has become available about the high rate of morbidity and mortality from this respiratory pathogen.

3 OBJECTIVES

3.1 Study Objectives

Primary:

1. To measure the nasal mucosal transcriptional responses to LAIV4 in the following age groups: 2-4 year old children, 9-13 year old children, and 18-49 year old adults.
2. To measure the B cell response to LAIV4 in the following age groups: 2-4 year old children, 9-13 year old children, and 18-49 year old adults.
3. To measure the B cell response to IIV4 in the following age groups: 6 month-4 year old children, 9-13 year old children, and 18-49 year old adults.

Secondary:

1. To compare the nasal mucosal transcriptional responses to LAIV4 between the different age groups.
2. To determine the evolution of B cell repertoire in young children after repeated immunization with different types of influenza vaccines.
3. To compare the B cell repertoire in response to LAIV4 versus IIV4 in different age groups.

3.2 Study Outcome Measures

3.2.1 Primary Outcome Measures:

- mRNA levels,
- Ig gene sequence

3.2.2 Secondary Outcome Measures:

- HAI titers
- PPAAb titer
- mAb reactivity

4 STUDY DESIGN

This is a Phase IV study of healthy children and adults who will receive the current seasonal influenza vaccine. There are no exclusions for gender, ethnicity or race. The volunteers will be enrolled into one of 7 groups over a 5 year period. Following confirmation of written informed consent and assent, immunization will be administered; blood samples and NP swabs for immunogenicity assays will be collected at various time points based on groups assigned. All volunteers will be followed for serious adverse events (SAEs).

Group A (LAIV4/annual return): Up to six 2-4 year old volunteers will be given a quadrivalent live, attenuated influenza vaccine (LAIV4). Blood samples to conduct the assays described will be taken at Day 0 pre-immunization and Day 6-8 post-Dose 1 for all children irrespective of those who require 1 dose (prior flu vaccination history) or 2 doses (vaccine-naïve). For children requiring 2 doses of vaccine, a second immunization will be given at Day 28-32 after Dose 1. All participants in this group will be asked to return annually for flu immunization and blood samples.

Group B (LAIV4/ single year): Up to twenty 2-4 year old volunteers will be given a quadrivalent live, attenuated influenza vaccine (LAIV4). Blood samples to conduct the assays described will be taken at Day 0 pre-immunization and Day 6-8 post-Dose 1 for all children irrespective of those who require 1 dose (prior flu vaccination history) or 2 doses (vaccine-naïve). For children requiring 2 doses of vaccine, a second immunization will be given at Day 28-32 after Dose 1.

Group C (LAIV4/NP swab group): Up to twenty 2-4 year old volunteers will be given a quadrivalent live, attenuated influenza vaccine (LAIV4). NP swabs will be collected at Day 1 and Day 21 post-Dose 1 for all children irrespective of those who require 1 dose or 2 doses of vaccine. For children requiring 2 doses of vaccine, a second immunization will be given at Day 28-32 after Dose 1. No blood will be collected for this group.

Group D (IIV4/annual return): Up to six 6 month-23 month old (inclusive) volunteers will be given a quadrivalent inactivated influenza vaccine (IIV4). Blood samples to conduct the assays described will be taken at Day 0 pre-immunization and Day 6-8 post-Dose 1 for children requiring 1 dose of vaccine (prior history of flu immunization). For children requiring 2 doses of vaccine (vaccine-naïve), a second immunization will be given at Day 28-32 after Dose 1. The second blood sample will be collected on Day 6-8 post-Dose 2. Volunteers will be asked to return annually for flu immunization and blood samples.

Group E (IIV4/single year): Up to twenty 6 month-23 month old (inclusive) volunteers will be given a quadrivalent inactivated influenza vaccine (IIV4). Blood samples to conduct the assays described will be taken at Day 0 pre-immunization and Day 6-8 post-Dose 1 for children requiring 1 dose of vaccine (prior history of flu immunization). For children

requiring 2 doses of vaccine (vaccine-naïve), a second immunization will be given at Day 28-32 after Dose 1. The second blood sample will be collected on Day 6-8 post- Dose 2. Volunteers will participate for single year.

Group F (LAIV4/single year) Up to forty 9-13 year old (n= 20) and 18-49 year old (n= 20) volunteers will be given a quadrivalent live, attenuated influenza vaccine (LAIV4). Blood samples and NP swabs will be collected. Blood samples will be taken at Day 0 pre-immunization, Day 6-8 post-immunization and Day 28±4 post-immunization. NP swabs will be collected at Day 1 post-immunization and Day 28 post –immunization. Children 9 yrs and older, and adults do not require a second dose of flu vaccine if previously unimmunized. Volunteers will participate for single year.

Group G (IIV4/single year) Up to forty, 9-13 year old (n= 20) and 18-49 year old (n= 20) volunteers will be given a quadrivalent inactivated influenza vaccine (IIV4). Blood samples to conduct assays will be taken at Day 0 pre-immunization, Day 6-8 post immunization and Day 28±4 post-immunization. No NP swabs will be collected for this group. Children 9 yrs and older, and adults do not require a second dose of flu vaccine if previously unimmunized. Volunteers will participate for single year.

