will be vaccinated with IIV4. Children who are vaccine-naïve will receive their Dose 1 of their vaccine at this visit. Volunteers will be observed in clinic for 15 minutes for any immediate serious reactions. Vaccine-naïve volunteers requiring Dose 2 will return at least 28 days post-Dose 1.

- A Memory Aid will be given to the volunteers/volunteer's parent with written and oral instructions for collection of information about serious adverse events. The memory aid is a simple diary for volunteer to record change in a health status and medications between study visits.
- The schedule for subsequent study visits will be reviewed.

7.3 Day 1 post- Dose 1 immunization for Group C and Group F only

- Review of medications and memory aid for serious adverse events
- Collect nasopharyngeal swab specimen; no blood sample will be collected at this visit.
- The schedule for subsequent study visits will be reviewed.

7.4 Day 6-8 post-Dose 1 immunization except Group C and vaccine-naïve volunteers in Group D and Group E requiring Dose 2; annually for Groups A and D.

- Review of medications and memory aid for serious adverse events
- Collect blood samples as follows:

All blood samples will be collected in heparinized, green top tubes to be picked up by the [name] lab for processing and analysis. For sample volumes >30 mL, one heparinized, green top tube will be sent to the HIMC if available ([name] lab requires at least 30 mL in heparinized, green top tubes at Day 6-8).

- For children weighing more than 100 lb., and from adults: total volume not to exceed 70 mL
 - From children weighing 66-100 lb: total volume not to exceed 30 mL
 - From children weighing 61-65 lb: total volume not to exceed 25 mL
 - From children weighing 41-60 lbs: total volume not to exceed 20 mL
 - From children weighing 16-40 lbs: total volume not to exceed 10 mL
 - From children 6 months through 35 months old, regardless of weight: Obtain a 4 mL blood sample into a heparin (green top) tube.
- The schedule for subsequent study visits will be reviewed for, Group F and G

- This will be the final visit for volunteers with prior influenza vaccination history in Group A, B, D and E. Complete Study Status form and Study Reimbursement form for these volunteers.

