10.3 Final Analysis Plan

In this proposal, the host innate immune responses to influenza virus infection will be examined within flow cytometry defined subsets of primary infected and bystander cells, as well as in bulk nasal mucosa RNA preparations. We have recently developed statistical models and methods that are appropriate to analyze transcriptional profiles following viral infection in high dimensional datasets. The basic approach that we propose is to obtain bulk measures at different hierarchical levels of the human nasal mucosa, including from sorted bulk populations and single cells from selected populations, and to identify significant innate response transcriptional signatures in the different age groups. Detailed procedures and analysis routines for analysis have been published recently and will be followed³⁶

We will obtain sequences of cognate heavy- and light-chain pairs and determine their V(D)J usage by analyzing them with IMGT HighV-QUEST. The heavy and light chains will be grouped according to their V-gene usage to clonal families of antibodies that use the same heavy-chain V(D)J and light-chain VJ sequences. Antibody phylogenetic trees will be generated based on the Ig sequences. The number, size, Ig gene usage, and isotype of clonally expanded Ig gene families, and in levels of somatic hypermutation and heterovariant cross-reactive Ab activity will be compared between the different vaccines and age groups.

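### In vaccine-naive Group D children the Day 6-8 sample follows Dose 2 in the first season and, by inference, a single dose in later seasons, so the first step of the within-child series mixes dose number with vaccine type and age

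*Combined protocol and SAP*

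**What the plan says.** Group D enrols up to six children aged 6-23 months, who receive IIV4 and come back each year. For those who are vaccine-naive, section 4 places Dose 2 at Day 28-32 and then states: "The second blood sample will be collected on Day 6-8 post-Dose 2. Volunteers will be asked to return annually". Section 7.4 sets the Day 6-8 post-Dose 1 visit for all participants "except Group C and vaccine-naïve volunteers in Group D and Group E requiring Dose 2; annually for Groups A and D". Section 7.7, the post-Dose 2 visit, carries no annual label. Section 7.6.1 takes no blood at the Dose 2 visit.

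Section 6.2 describes a two-dose course only for children through age 8 with no earlier influenza vaccination. The Protocol Summary ties return-year vaccination to ACIP guidance and gives no dose count. A footnote to Appendix A moves Group D children to LAIV4 once they reach age 2, barring a contraindication.

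The objective these children serve is secondary objective 2 in section 3.1: "To determine the evolution of B cell repertoire in young children after repeated immunization with different types of influenza vaccines". The Protocol Summary lists a related aim, IIV first and LAIV4 afterwards, as primary objective 5. On analysis, section 10.3 says only that the repertoire features "will be compared between the different vaccines and age groups". It describes no within-child comparison over seasons and does not mention dose number.

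**The concern.** A series meant to show how a child's B cell repertoire evolves should compare like samples. Here the first Day 6-8 point is a response to a second dose about four weeks after priming. Later points are responses to one dose about a year after the last. Section 2.1 argues that memory B cells present before vaccination shape the response, and section 10.1 singles out first and second exposures. By the protocol's own reasoning, dose number can affect the outcome.

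For many of these children the change in dose number falls on the same step as the change from IIV4 to LAIV4. A shift in the number or size of clonal families, isotype or somatic hypermutation could then be reported as an effect of changing vaccine type when part of it comes from dose number. The season-1 sample also has no blood drawn just before the sampled dose, whereas in return seasons Day 0 supplies it.

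**Working it through.** The plan gives no figure to reproduce. The check uses the visit windows, the dose rules and the entry ages.

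**1. Dose count in return seasons.** A naive entrant has been vaccinated by the first return. Under section 6.2 the two-dose course no longer applies, and Appendix A then places the child in the row for prior vaccination: one dose, with blood at Day 6-8 post-Dose 1. The annual label on 7.4 and its absence from 7.7 agree with this. It is an inference from several sections; no single sentence says it.

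**2. Timing of the post-vaccination sample in naive entrants.**

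| | Season 1 | Return seasons |
|---|---|---|
| Days from Day 0 | 28 + 6 = 34 to 32 + 8 = 40 | 6 to 8 |
| Days since latest dose | 6 to 8 | 6 to 8 |
| Doses that season before the sample | 2 | 1 |

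The interval from baseline shortens by 34 - 8 = 26 to 40 - 6 = 34 days.

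**3. Doses received by the time of the sample, seasons 1 to 5, with one dose in each return season.**
- Group D, naive: 2, 3, 4, 5, 6 cumulative; 2, 1, 1, 1, 1 within season.
- Group A, naive, sampled after Dose 1 every year: 1, 3, 4, 5, 6 cumulative; 1, 1, 1, 1, 1 within season.

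**4. Overlap with the vaccine switch.** Entry ages of 6 to 23 months give 18 monthly ages. Assume they are equally likely. The share aged 24 months or more at the first return is:
- 12-month interval: entry at 12-23 months, 12/18 = 67%.
- 8-month interval: entry at 16-23 months, 8/18 = 44%.
- 16-month interval: entry at 8-23 months, 16/18 = 89%.

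The 8 and 16 month limits assume that returns fall in the same August to December window as enrolment (December to August; August to December of the next year).

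**The case against.** The best defence is that sampling always follows the last required dose by 6-8 days. Section 2.1 treats the plasmablast response as a picture of recent antigen exposure, and on that measure the window never moves. This stands as far as it goes. A reader might infer from 34-40 days against 6-8 days that blood is taken much later after vaccination in season 1. The documents do not support that, because those figures count from Day 0. However, no such sampling rule is stated, Group A follows a different one, and equal days since the last dose do not make a boost at four weeks equivalent to a recall at about a year.

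It can also be said that a naive child's first season must differ from later ones, and that age, cumulative exposure and vaccine type change together under any sampling rule. That is true. Dose number is one more factor in a step that six children could not resolve in any case. Since 10.3 specifies no longitudinal model, no stated analysis is shown to be biased; the gap is that nothing warns against the naive reading.

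A reader might go further and start the Day 6-8 trend at the first single-dose season. The documents argue against this. For a child who switches in season 2, the season-1 post-Dose 2 sample is the only one taken after IIV4, and dropping it would remove the contrast the objective needs.

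**Conclusion.** The point holds as a limit on interpretation. In naive Group D children the season 1-to-2 step in the Day 6-8 repertoire confounds dose number with age and, for roughly two thirds of entrants (range 44-89%), with vaccine type.

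This rests on three assumptions: one dose in each return season, which ACIP guidance or a missed Dose 2 could alter; uniform entry ages; and naive children having the same ages as all entrants. If naive children are younger, the overlap is smaller.

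It might be inferred that the whole Group D series is affected. That is not established: inclusion criterion 6 admits children with one prior IIV season, who are sampled after a single dose from the start, and the number of naive children is not given. The study is exploratory with no confirmatory test, so this is an inexpensive improvement to the analysis plan and does not undermine the design.

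**What to change.** In section 10.3:
- Add a within-child, across-season comparison of the Day 0 samples. They precede vaccination in every season, for naive and previously vaccinated children alike, and address the pre-vaccination memory repertoire whose evolution section 2.1 calls unknown.
- Keep all Day 6-8 samples, including season-1 post-Dose 2, and report them stratified by in-season and cumulative dose number.
- State that the season 1-to-2 step confounds dose number, vaccine type and age, and is not to be read as the effect of any one of them.

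Separately, exclusions 2 and 3 in section 5.2 (LAIV in the prior season; influenza vaccination in two or more prior seasons) stand under a heading that also covers later annual vaccinations. Read literally, exclusion 3 would stop a naive entrant after season 2. These passages and the annual-return design must be reconciled, because they determine how long the series can be.

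The cost is wording and a dose-number label on each sample, which the visit records already allow; any extra sequencing uses blood already drawn. The drawback is that Day 0 blood, 4 mL in children under 36 months, holds few plasmablasts. That series will rest mainly on memory B cells and will be imprecise.
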